### 6.15.2. Adverse Events

Adverse events are recorded in the eCRFs. Each AE will be coded to system organ class (SOC) and preferred term (PT) using the Medical Dictionary for Regulatory Activities (MedDRA) version that is current at the time of database lock. Severity of AEs is recorded as mild, moderate, or severe.

A TEAE is defined as an event that either first occurred or worsened in severity after the first dose of study treatment and on or prior to the last visit date during the analysis period. The analysis period is defined as the treatment period plus up to 30 days off-drug follow-up time.

Adverse events are classified based upon the MedDRA PT. The MedDRA Lowest Level Term (LLT) will be used in defining which events are treatment-emergent. The maximum severity for each LLT during the baseline period up to first dose of the study medication will be used as baseline. If an event with missing severity is preexisting during the baseline period, and persists during the treatment period, then the baseline severity will be considered mild for determining treatment-emergence (that is, the event is treatment-emergent if the severity is coded moderate or severe postbaseline and not treatment-emergent if the severity is coded mild postbaseline). If an event occurring postbaseline has a missing severity rating, then the event is considered treatment-emergent unless the baseline rating is severe, in which case the event is not treatment-emergent. The day and time for events where onset is on the day of the first dose of study treatment will both be used to distinguish between pretreatment and posttreatment to derive treatment-emergence. Should there be insufficient data for AE start date to make this comparison (for example, the AE start year is the same as the treatment start year, but the AE start month and day are missing), the AE will be considered treatment-emergent.

In general, summaries will include the number of patients in the safety population (N), frequency of patients reporting the event (n), and relative frequency (that is, percentage;  $n/N*100$ ). For any events that are gender-specific based on the displayed PT, the denominator used to compute the percentage will only include patients from the appropriate gender.

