### **Herpes zoster**

Cases of herpes zoster will be further classified as follows:

- localized or non-multidermatomal-involvement of the primary and/or adjacent dermatomes only
  - complicated – documented ocular (cornea or deeper structure; for example, iritis, keratitis, retinitis, etc.) or motor nerve involvement (e.g., palsy; post herpetic neuralgia [PHN] does not meet criteria for motor nerve involvement).
  - uncomplicated-localized or non-multidermatomal cases that are not complicated
- multidermatomal-involvement beyond primary and adjacent dermatomes (that is, >3 contiguous dermatomes) or involvement of two or more non-contiguous dermatomes
  - complicated-documented ocular (cornea or deeper structure; for example iritis, keratitis, retinitis, etc.) or motor nerve involvement
  - uncomplicated-multidermatomal cases
- disseminated-systemic infection, visceral or widespread cutaneous (e.g.,  $\geq 5$  dermatomes or 3 to 4 dermatomes including at least 1 non-contiguous).

- Recurrent - >1 infection occurring in an individual patient during the course of participation in the baricitinib clinical program.

All herpes zoster will undergo medical review to determine the classification as described above.

A summary of herpes zoster table will be provided. The summary table will also include event maximum severity, seriousness, whether resulting in temporary study drug interruption, whether resulting in study drug discontinuation, whether treated with antiviral medication, and event outcome. The incidence rate adjusted for observation time will also be provided (as defined in Section 6.15.2). Of note, in the context of herpes zoster, antiviral medication treatment is defined as that the medication was initiated at the event start date, or within 30 days before or after the event start date. The antiviral medication for herpes zoster includes but not limited to Aciclovir, Brivudine, Cidofovir, Famciclovir, Foscarnet, Ganciclovir, Penciclovir, Valaciclovir, Valganciclovir, Vidarabine (best presented by J05AB, J05AC, J05AE, and J05AH Anatomical Therapeutic Classification codes). Medical representatives will review the concomitant medication list prior to database lock and make adjustment of the above list if necessary.

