If a patient has more than 1 event of herpes zoster, the event with the maximum severity will be used in these summary tables. If more than 1 event of herpes zoster occurs with the same severity, the event with the longest duration will be used in the summary table.

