### **Herpes simplex**

A summary analysis of herpes simplex will be provided. Herpes simplex will be defined based on MedDRA PT as listed in the compound level safety standards (both narrow and broad terms in the herpes simplex section). The list needs to be reviewed by medical prior to data locks (final and interim). The summary table will include event maximum severity, seriousness, whether resulting in temporary study drug interruption, whether resulting in study drug discontinuation, and whether treated with antiviral medication.

If a patient has more than 1 event of herpes simplex, the event with the maximum severity will be used in these summary tables. If more than 1 event of herpes simplex occurs with the same severity, the event with the longest duration will be used in the summary table.

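### The herpes zoster and herpes simplex tables read seriousness, interruption, discontinuation and antiviral treatment from one event per patient chosen on severity, so these rows can understate the patient counts

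*SAP*

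**What the plan says.** SAP 6.15.5.6 plans one summary table for herpes zoster and one for herpes simplex. For zoster: "The summary table will also include event maximum severity, seriousness, whether resulting in temporary study drug interruption, whether resulting in study drug discontinuation". The same sentence goes on to antiviral treatment and event outcome. The simplex table carries the same items except outcome.

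Patients with several events are reduced to one. For zoster: "If a patient has more than 1 event of herpes zoster, the event with the maximum severity will be used in these summary tables". The tie-break is: "If more than 1 event of herpes zoster occurs with the same severity, the event with the longest duration will be used in the summary". The simplex text has the same selection rule: "If a patient has more than 1 event of herpes simplex, the event with the maximum severity will be used in these summary tables". Its tie-break is also the same: "If more than 1 event of herpes simplex occurs with the same severity, the event with the longest duration will be used in the summary". Neither text exempts any row or provides a flag for any event.

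On the selecting attribute, SAP 6.15.2 says: "Severity of AEs is recorded as mild, moderate, or severe". Seriousness is defined separately in SAP 6.15.2.2, by outcomes such as death or hospitalization. The zoster text also defines a recurrent class for patients with more than one infection, so repeat events are foreseen.

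**The concern.** Severity is a three-level clinical rating. Seriousness depends on outcome, and interruption, discontinuation and antiviral treatment are actions taken. An event chosen because it was rated most severe need not be the one that was serious or led to an action. When it is not, the patient appears in the table without an attribute that the patient did have.

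The error runs one way only. The selected event is one of the patient's own events, so a yes in the table is always true, while a no may be false.

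Infections, with herpes zoster named, are adverse events of special interest in Protocol 9.2.2, and these two tables are where a reader will look for the herpes picture. The SAP counts seriousness, discontinuation and interruption per patient on any event in 6.15.2.2 and 6.15.2.3, and counts serious infections and infections leading to permanent discontinuation at the start of 6.15.5.6. The herpes tables could show fewer such patients than those outputs, and the SAP gives the reader no explanation.

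**Working it through.** The plan states no figure on this point, so there is none to reproduce. The check applies the written rule and compares it with an any-event count.

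**Inputs.** The selection rule, tie-break and table rows come from SAP 6.15.5.6, the severity scale from SAP 6.15.2, the definition of seriousness from SAP 6.15.2.2, the zoster hold from Protocol Table JAIY.4, and the planned 100 patients per arm from SAP 5.1. The documents give no rate for herpes events or for repeat events, so every rate below is an assumption.

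**1. Three two-event patients under the rule.**
- Event A is moderate, serious, and led to interruption and discontinuation. Event B is severe, not serious, with no action taken. The rule picks B. The table shows no for all three attributes, and the any-event answer is yes for all three.
- Both events are moderate. A is serious and lasts 7 days; B is not serious and lasts 12 days. The rule picks B and seriousness is lost.
- A is moderate and serious and lasts 7 days; B is mild and lasts 40 days. The rule picks A and nothing is lost.

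**2. The mechanism, enumerated.** Take two events of which exactly one carries the attribute. There are 3 × 3 severity pairs and 2 duration orders, so 18 orderings. The attribute is lost when the other event is more severe (3 pairs × 2 orders = 6) or equally severe and longer (3 pairs × 1 order = 3), in total 6 + 3 = 9 of 18. This shows how the loss arises; it does not predict a frequency.

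**3. Patients misclassified per arm and attribute.** The expected number is m × q × r, where m is the number of patients per 100-patient arm with two or more events (assumed 1 to 5), q is the share of those with exactly one event carrying the attribute (assumed 10% to 30%), and r is the chance that this event is displaced (assumed 10% to 50%).
- Low end: 1 × 0.10 × 0.10 = 0.01.
- High end: 5 × 0.30 × 0.50 = 0.75.

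**4. Share of true cases credited.** Suppose each of k events carries the attribute with probability p, independently of the other events and of which event is selected. The share credited is p / (1 − (1 − p)^k).
- For p from 0.05 to 0.30, this is 51% to 59% with k = 2 and 35% to 46% with k = 3.
- Illustration: 4 two-event patients with p = 0.20 give 4 × 0.20 = 0.8 shown against 4 × (1 − 0.8²) = 1.44 true, a shortfall of 0.64.
- The loss is smaller if the attribute tracks severity.

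**5. Zoster interruption.** Table JAIY.4 holds investigational product for any symptomatic zoster, without reference to severity, so p should be high for this row. With p = 0.90 assumed and k = 2, the share credited is 0.90 / (1 − 0.1²) = 0.90 / 0.99 = 91%. The range in step 4 does not describe this row.

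**The case against.** Using one representative event per patient is an explicit, prespecified choice, and it keeps every row of the table describing an event that occurred. A mix of worst values can describe a composite that never did. The tables are descriptive and lie outside the multiplicity-controlled tests. Treatment lasts 16 weeks. Entry criteria exclude recent or repeated eczema herpeticum, recent symptomatic or previously complicated zoster, and herpes simplex symptomatic at randomization, so patients with several events should be few.

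The smallness stands. The coherence argument justifies taking severity and outcome from one event; it does not justify rows on an adverse event of special interest that can only err downwards.

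A reader might also infer more than the documents support:
- **That the events disappear from the report.** They do not. 6.15.2.2 and 6.15.2.3 summarize and list serious events, discontinuations and interruptions, and the infections overview counts serious infections and infections leading to permanent discontinuation. The understatement is confined to the two herpes tables.
- **That a longer event displaces a serious one in general.** Duration acts only at equal severity, as the third patient in step 1 shows.
- **That the outputs will disagree.** They can. It takes a patient with at least two events whose attributes differ, and the attribute must sit on the event not selected.
- **That the loss will be larger on baricitinib.** It grows with events per patient, but the documents give no rates by arm from which to say so.
- **That the zoster extent classes are part of the same fault.** The cutaneous examples of disseminated disease (five or more "dermatomes or 3 to 4 dermatomes including at least 1 non-contiguous") also meet the multidermatomal definition, and no order of precedence is written. That is a separate, minor clarification, since every zoster case goes to medical review for classification.

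**Conclusion.** The point holds for both tables as written. Seriousness, interruption, discontinuation and antiviral treatment are read from an event chosen on another attribute, so the number of patients with each can be understated and never overstated.

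The effect is probably below one patient per arm per attribute: 0.01 to 0.75 under the ranges in step 3, all of which are assumed. It is smallest for zoster interruption. It is still worth correcting, because serious or discontinuing herpes cases may number only a few per arm, and one patient can then change how the row reads.

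**What to change.** In both herpes subsections of SAP 6.15.5.6:
- Keep the maximum-severity event, with the duration tie-break, for the severity row. For zoster, keep it also for the outcome row, labelled as the outcome of that event.
- Count a patient as yes on seriousness, temporary interruption, discontinuation and antiviral treatment if any of the patient's herpes events of that type qualifies.
- Show the number of events alongside the number of patients.

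This costs a short change to the text of each subsection and a simple programming change, with no new data and no effect on efficacy analyses or patient management. The one drawback is that the rows no longer all describe a single event, so each table needs a footnote saying which rows rest on the most severe event and which on any event.

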### **Herpes simplex**

A summary analysis of herpes simplex will be provided. Herpes simplex will be defined based on MedDRA PT as listed in the compound level safety standards (both narrow and broad terms in the herpes simplex section). The list needs to be reviewed by medical prior to data locks (final and interim). The summary table will include event maximum severity, seriousness, whether resulting in temporary study drug interruption, whether resulting in study drug discontinuation, and whether treated with antiviral medication.

If a patient has more than 1 event of herpes simplex, the event with the maximum severity will be used in these summary tables. If more than 1 event of herpes simplex occurs with the same severity, the event with the longest duration will be used in the summary table.

### **Skin Infections**

A summary analysis of skin infections may be provided. Skin infections may be defined based on MedDRA preferred term (see the Compound level safety standards).

### **HBV DNA**

A listing of patients with detectable hepatitis B virus (HBV) deoxyribonucleic acid (DNA) post baseline will be provided.

HBV DNA status post baseline (not detectable, detectable but not quantifiable [i.e., < lower limit of detection (LLOD)], quantifiable [i.e., ≥LLOD]) will be summarized by treatment group stratified by baseline HBV serology status, specifically:

- HBsAb+ / HBcAb+

- HBsAb- / HBcAb+

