8.1.2. Permanent Discontinuation from Investigational Product

Investigational product should be permanently discontinued if the patient requests to discontinue investigational product.

Discontinuation of the investigational product for abnormal liver tests should be considered by the investigator when a patient meets 1 of the following conditions after consultation with the Lilly-designated medical monitor:

- ALT or AST >8x ULN
- ALT or AST >5x ULN for more than 2 weeks
- ALT or AST >3x ULN and total bilirubin level (TBL) >2x ULN or international normalized ratio (INR) >1.5

- ALT or AST >3x ULN with the appearance of fatigue, nausea, vomiting, right upper-quadrant pain or tenderness, fever, and/or rash
- ALP >3x ULN
- ALP >2.5x ULN and TBL >2x ULN
- ALP >2.5x ULN with the appearance of fatigue, nausea, vomiting, right quadrant pain or tenderness, fever, and/or rash

NOTE: Patients who are discontinued from investigational product due to a hepatic event or liver test abnormality should have additional hepatic safety data collected via the hepatic safety eCRF.

Investigational product should be permanently discontinued if any of the following laboratory abnormalities are observed:

- white blood cell count <1000 cells/ μ L ($1.00 \times 10^3/\mu$ L or 1.00 GI/L)
- ANC <500 cells/ μ L ($0.50 \times 10^3/\mu$ L or 0.50 GI/L)
- lymphocyte count <200 cells/ μ L ($0.20 \times 10^3/\mu$ L or 0.20 GI/L)
- hemoglobin <6.5 g/dL (<65.0 g/L)

NOTE: Temporary interruption rules (Section 8.1.1) must be followed where applicable. For laboratory values that meet permanent discontinuation thresholds, investigational product should be discontinued. However, if in the opinion of the investigator the laboratory abnormality is due to intercurrent illness such as cholelithiasis or another identified factor, laboratory tests may be repeated. Only when the laboratory value meets resumption thresholds (Table JAIY.4) following the resolution of the intercurrent illness or other identified factor, may the investigator restart investigational product, after consultation with the Lilly-designated medical monitor.

In addition, patients will be discontinued from investigational product in the following circumstances:

- pregnancy
- malignancy (except for successfully treated basal or squamous cell skin carcinoma)
- hepatitis B virus DNA is detected with a value above limit of quantitation or 2 sequential tests return a value of below the limit of quantitation (Section 9.4.8)

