9.4.8. Hepatitis B Virus DNA Monitoring

Patients who are HBcAb positive and HBV DNA negative (undetectable) at Visit 1 will require measurement of HBV DNA at Week 16 (Visit 8) or early termination visit, regardless of their hepatitis B surface antibody (HBsAb) status.

The following actions should be taken in response to HBV DNA test results:

- If a single result is obtained with a value “below limit of quantitation,” the test should be repeated within approximately 2 weeks. If the repeat test result is “target not detected,” monitoring will resume for those patients enrolling in the long-term extension study, JAHN.
- If the patient has 2 or more test results with a value “below limit of quantitation” or a test result above the limit of quantitation, the patient will be permanently discontinued from investigational product (Section 8.1.2) and should be referred to a hepatology specialist.

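### The SAP's HBV DNA table cuts its categories at the limit of detection, contradicting its own labels and the protocol's limit of quantitation

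*SAP*

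**What the plan says.** Section 6.15.5.6 of the SAP, under HBV DNA, commits to two outputs. The first is a listing: "A listing of patients with detectable hepatitis B virus (HBV) deoxyribonucleic acid (DNA) post baseline will be provided". The second is a summary by treatment group, stratified by baseline hepatitis B serology, in three status categories. The category not detectable has no cut-point. The middle category is "detectable but not quantifiable [i.e., < lower limit of detection (LLOD", and the last, quantifiable, is defined as at or above the same LLOD. The abbreviation LLOD is spelled out as a detection limit and used for both cut-points. Neither document redefines it as a quantitation limit.

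The protocol works with the limit of quantitation. Section 9.4.8 states "Patients who are HBcAb positive and HBV DNA negative (undetectable) at Visit 1 will require measurement of HBV DNA at Week 16 (Visit 8") or at early termination. After a single result below the quantitation limit, "the test should be repeated within approximately 2 weeks", and a repeat on which the target is not detected is named as a separate outcome. Where there are two or more results below the quantitation limit, "or a test result above the limit of quantitation, the patient will be permanently discontinued from investigational product". Section 8.1.2 uses the same limit: a value above it, or the case where "2 sequential tests return a value of below the limit of quantitation".

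**The concern.** The words in the brackets do not define what the labels say. A measurement below the detection limit is, by the meaning of the term, not detected, so it cannot belong to a category labelled detectable. The cut-point between the second and third categories also differs from the one by which the protocol classifies the same laboratory results.

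The table is a committed safety output. It covers core-antibody-positive patients, who may be enrolled if HBV DNA is negative and are then tested again. A programmer who follows the brackets could report a low-level detected result as quantifiable, and a reader of the study report would see more quantifiable HBV DNA than the laboratory found. Such patients are likely to be few, so one misplaced result could visibly change a row.

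**Working it through.** No sample size, power or alpha figure is involved, and the plan states no number to reproduce. The check places every possible result in the SAP's categories and compares the outcome with the labels and with the protocol.

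Inputs:
- SAP cut-points (Section 6.15.5.6, HBV DNA): below LLOD, and at or above LLOD.
- Protocol result types (Sections 8.1.2 and 9.4.8): target not detected, below the limit of quantitation, above the limit of quantitation.
- Assumption: the assay's limit of detection (LOD) is lower than its limit of quantitation (LOQ). The documents give neither value.

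Let x be the HBV DNA result.

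| Range of x | Category by the SAP's brackets | Category by the SAP's labels | Protocol result type |
|---|---|---|---|
| x < LOD | Meets the bracket of the middle category, and is also not detectable | Not detectable | Target not detected |
| LOD ≤ x < LOQ | Quantifiable | Detectable but not quantifiable | Below the limit of quantitation |
| x ≥ LOQ | Quantifiable | Quantifiable | Above the limit of quantitation |

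Reading the rows:

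1. In the first row the label and the bracket of the middle category cannot both hold. If a result must satisfy both, the category is empty by definition. If the bracket alone decides, the category takes in undetectable results and overlaps with not detectable.
2. In the second row a detected result below the quantitation limit meets the bracket for quantifiable, against the SAP's own label and the protocol's result type.
3. In the third row brackets, labels and protocol agree.

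The number of misplaced detected results therefore equals the number with LOD ≤ x < LOQ. It runs from 0, if the two limits coincide or no such result occurs, up to every detected result below the quantitation limit.

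Repeating the check with the lower limit of quantitation (LLOQ) in both brackets, the first row is not detectable, the second is detectable but below LLOQ, and the third is at or above LLOQ. The categories are then exclusive and exhaustive, none is empty by definition, and each corresponds to one protocol result type.

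**The case against.** The strongest reply is that this is a slip in an abbreviation. The three labels are correct and already correspond to the protocol's result types; only the bracketed explanation is wrong. The protocol puts the terms for a sub-quantifiable and an undetected result in quotation marks, which suggests that the laboratory reports them as text. A table built from that text would misplace nothing. This stands, and it makes the consequence conditional. It does not make the definition right, because a prespecified category should not depend on a programmer ignoring its written cut-point.

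A second reply also stands. A reader might infer that the table would show patients as having met a discontinuation criterion when they had only qualified for a repeat test. The documents do not support that as a general statement. Sections 8.1.2 and 9.4.8 attach permanent discontinuation both to a value above the quantitation limit and to two results below it, so a sub-quantifiable result can lead to either action. The table reports HBV DNA status, and even when corrected it would not map one-to-one to protocol actions.

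Third, the reach is small. Scheduled post-baseline testing takes place only at Week 16 or early termination, and the Schedule of Activities dispenses no investigational product at Visit 8. The listing does not use the disputed cut-point, so no detected case is lost from reporting.

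**Conclusion.** The definition is wrong as written: the bracketed cut-points contradict the SAP's own labels and differ from the limit that the protocol uses. Misclassification in the table follows only if the brackets are what is programmed and the assay's detection limit is below its quantitation limit. Under those two conditions, detected results below the quantitation limit are tabulated as quantifiable, and the middle category is empty or overlaps with not detectable.

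It would be tempting to say that all results between the two limits are misclassified. That goes too far: the text contradicts itself without settling whether label or bracket governs, and no assay limits are given. The number affected is unknown and may be zero.

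This is a minor point of drafting in a descriptive safety table. It has no bearing on efficacy, alpha or sample size.

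**What to change.** In SAP Section 6.15.5.6, HBV DNA, replace LLOD with the lower limit of quantitation in both brackets: detectable but below LLOQ, and quantifiable at or above LLOQ. It would also help to state that not detectable means a laboratory result of target not detected. This reconciles the SAP with protocol Sections 8.1.2 and 9.4.8.

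The cost is one corrected term in two places, plus a check that the table program uses the same definition. No data collection, analysis method or clinical rule changes.
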